1 SYNOPSIS

NAME OF SPONSOR: Genmab A/S PROTOCOL No.: GEN702

NAME OF TRIAL TREATMENT: Tisotumab vedotin (HuMax®-TF-ADC)

TITLE OF TRIAL: Dose-escalating and cohort expansion safety trial of tissue factor specific antibody drug conjugate tisotumab vedotin (HuMax®-TF-ADC) in patients with locally advanced and/or metastatic solid tumors known to express tissue factor

TRIAL CENTERS: The Dose Escalation part of the trial is planned to be performed in a maximum of three sites in Denmark, the United Kingdom (UK) and the United States of America (USA). The Cohort Expansion part of the trial is planned to be performed in the ongoing countries and in Hungary and potentially Belgium.

TRIAL PERIOD: A Dose Escalation part will be followed by a Cohort Expansion part. The trial will be stopped when the last patient included in the Cohort Expansion part completes the trial or when the last ongoing patient has discontinued treatment and attended the Safety follow-up Visit, whichever occurs first.

PHASE OF
DEVELOPMENT:
Dose Escalation part:
Phase I
Cohort Expansion part:
Phase II

PLANNED TRIAL DATES: Enrollment period is planned to last approximately 21 months.

OBJECTIVES:

Primary Trial Objective: To establish the tolerability of HuMax® tissue factor antibody drug conjugate tisotumab vedotin [HuMax-TF-ADC]) dosed three times every four weeks (3q4wk) in a mixed population of patients with specified solid tumors.

Secondary Trial Objective(s):

- To determine the maximum tolerated dose (MTD) and the recommended dose for phase II trials (RP2D) with tisotumab vedotin (HuMax-TF-ADC) dosed 3q4wk.
- To establish the pharmacokinetic (PK) profile of tisotumab vedotin (HuMax-TF-ADC) dosed 3q4wk.
- To evaluate the anti-tumor activity of tisotumab vedotin (HuMax-TF-ADC) dosed 3q4wk in a mixed population of patients with specified solid tumors.

TRIAL DESIGN AND METHODOLOGY:

The trial is a safety trial of HuMax-TF-ADC dosed 3q4wk (Days 1, 8 and 15 of each 28-day cycle) in a mixed population of patients with solid tumors known to express tissue factor (TF) and where the use of systemically administered tubulin inhibitors is part of standard of care (SoC). The trial consists of two parts, an open-label, multicenter, phase I, Dose Escalation part, followed by an open-label phase II Cohort Expansion part.

The Dose Escalation part is a standard 3 (+3) design. In each dose cohort, the initial three patients must include at least two different cancer types. A maximum of three dose levels is anticipated. Patients may receive up to 12 cycles of treatment.

The Cohort Expansion part will have a parallel group design, with a minimum of 20 and a maximum of 30 patients in two or three indication arms. Patients in the Cohort Expansion part will be treated with the RP2D from the Dose Escalation part. Patients may receive up to nine cycles of treatment.

A Data Monitoring Committee (DMC) will evaluate safety data during the Dose Escalation part of the trial and will convene in the event of safety signals in the Cohort Expansion part of the trial.

Severe ocular toxicity has been observed at 1.2 mg/kg 3q4wk (the RP2D for the Cohort Expansion part), and an urgent safety Protocol Amendment 4.0 has been implemented. Patients will not further receive the dosing schedule 3q4wk; instead tisotumab vedotin 2.0 mg/kg will be administered once every three weeks (q3wk).

TRIAL POPULATION AND MAIN CRITERIA FOR INCLUSION/EXCLUSION:

The patient population in the Dose Escalation part will encompass patients with advanced (locally advanced and/or metastatic) cancer of the ovary, cervix, endometrium, bladder, prostate (castration-resistant prostate cancer [CRPC]), esophagus or lung (non-small cell lung cancer [NSCLC]) who have failed available standard

Final 5.0 (incorporating Protocol Amendment 4) 06 Jul 2017

treatments or who are not candidates for standard therapy. The specific indications for the Cohort Expansion part will be decided once the RP2D has been determined from the Dose Escalation part.

Patients cannot be enrolled before all inclusion criteria (including test results) are confirmed.

Inclusion Criteria:

- For the Dose Escalation part: Patients with relapsed, advanced and/or metastatic cancer of the ovary, cervix, endometrium, bladder, prostate, esophagus, or NSCLC who have failed available standard treatments or who are not candidates for standard therapy.
- For the Cohort Expansion part: The specific indications for the Cohort Expansion part will be decided once the RP2D has been determined. After implementation of the urgent safety measure (Protocol Amendment 4), no patients will further receive the 3q4wk schedule; instead, tisotumab vedotin (HuMax-TF-ADC) 2.0 mg/kg will be administered once q3wk.
- Patients with relapsed, advanced and/or metastatic cancer of the ovary, cervix, endometrium, bladder, prostate, esophagus, or NSCLC who have failed the following anti-cancer therapy:
 - Bladder cancer (including urothelial carcinomas [transitional cell carcinomas] regardless of the initial site of origin of the tumor: renal pelvis, ureter or bladder lumen): failing platinum-based therapy. Patients must have received no more than three prior treatment regimens for advanced disease.
 - CRPC: failing docetaxel and either abiraterone OR enzalutamide. Patients must have received
 no more than two prior chemotherapy-based regimens and a maximum of six prior treatment
 regimens for advanced disease.
 - Ovarian cancer: resistant to at least one platinum-based therapy and after failing at least one line of taxane-containing therapy (isolated CA 125 progression does NOT qualify for trial entry). Patients with primary platinum refractory disease are excluded. Patients must have received no more than five prior treatment regimens for advanced disease.
 - O Cervical cancer: failing a platinum-based regimen. Patients must have received no more than four prior treatment regimens for advanced disease.
 - o Endometrial cancer: failing platinum-based therapy. Patients must have received no more than four prior treatment regimens for advanced disease (excluding adjuvant chemotherapy).
 - Esophageal cancer (esophageal cancer or gastro-esophageal junction cancer): failing
 platinum-based therapy with or without taxanes depending on established SoC therapy. Patients
 must have received no more than three prior treatment regimens for advanced disease.
 - NSCLC: failing at least one platinum-based regimen. Patients with epidermal growth factor receptor (EGFR) or anaplastic lymphoma kinase mutations should have been treated with appropriate targeted therapy before trial entry. Patients must have received no more than four (five allowed for patients with EGFR mutated adenocarcinomas) prior treatment regimens for advanced disease.
- Patients must have measurable disease according to RECIST (Response Evaluation Criteria In Solid Tumors) version 1.1.
 - o A minimum of 1 lesion \geq 10 mm in the longest diameter from a non-irradiated area;
 - Lymph nodes lesion ≥ 15 mm in the shortest diameter from a non-irradiated area.
 - O Patients with prostate cancer must be clinically refractory and resistant to hormone therapy as documented by progression (CRPC) and can be included based on prostate specific antigen (PSA) and/or bone metastases according to the Prostate Cancer Working Group Guideline.
 - O Patients with ovarian cancer can be included based on CA 125 positivity according to the Gynaecologic Cancer Intergroup Guideline. This is only applicable for the Dose Escalation part of the trial.
- Age \geq 18 years.
- Acceptable renal function: glomerular filtration rate (Cockroft-Gault) > 45 mL/ min.

Final 5.0 (incorporating Protocol Amendment 4) 06 Jul 2017

- Acceptable liver function defined as: alanine aminotransferase (ALT) and aspartate aminotransferase (AST) ≤ 3 times the upper limit of normal (ULN) (if liver tumor/ metastases are present, then ≤ 5 × ULN is allowed); bilirubin ≤ 1.5 × ULN, except in patients diagnosed with Gilbert's syndrome, direct bilirubin < 2 × ULN.
- Acceptable hematological status (hematologic support is allowed if administered at least one week before Cycle 1 Day 1) defined as: hemoglobin \geq 5.6 mmol/L (\sim 9 g/dL), absolute neutrophil count (ANC) \geq 1500/µL (1.5× 10⁹/L); platelet count \geq 100 ×10⁹/L.
- Acceptable coagulation status defined as: international normalized ratio (INR) ≤ 1.2 (without anticoagulant therapy), and activated partial thromboplastin time (aPTT) \leq ULN.
- Eastern Cooperative Oncology Group (ECOG) performance status of 0 or 1.
- Life expectancy of at least three months.
- A negative serum pregnancy test (if female and aged between 18-55 years old). Women who are pregnant or breast feeding are not to be included.
- Patients, both females and males, of reproductive potential must agree to use adequate contraception during and for six months after the last infusion of tisotumab vedotin (HuMax-TF-ADC).
 - Adequate contraception for women is defined as hormonal birth control or an intrauterine device. In countries where two highly effective methods of contraception are required this will be an inclusion criterion.
 - Male patients must be willing to use a latex condom during any sexual contact with females of childbearing potential during and for six months after the last infusion of tisotumab vedotin (HuMax-TF-ADC), even after having undergone a successful vasectomy. It is recommended that fertile males consider having semen specimen obtained for storage for potential future conception.
- Following receipt of verbal and written information about the trial, patients must provide signed informed consent before any trial-related activity is carried out.

Kev Exclusion Criteria:

- Hematological: known past or current coagulation defects leading to an increased risk of bleeding; diffuse alveolar hemorrhage from vasculitis; known bleeding diathesis; ongoing major bleeding; trauma with increased risk of life-threatening bleeding or history of severe head trauma or intracranial surgery within two months of trial entry.
- Cardiovascular: clinically significant cardiac disease (including unstable angina, acute myocardial infarction within six months of the Screening Visit, known congestive heart failure [Grade III or IV as classified by the New York Heart Association], and/or a known decreased cardiac ejection fraction of < 45%); a baseline QT interval as corrected by Fridericia's formula (QTcF) > 450 msec, a complete left bundle branch block (defined as a QRS interval ≥ 120 msec in left bundle branch block form) or an incomplete left bundle branch block.
- Excluded medications or treatment regimens: therapeutic anti-coagulative or long-term anti-platelet treatment (use of low dose acetylsalicylic acid [ASA] up to 81 mg/day and non-ASA nonsteroidal anti-inflammatory drugs [NSAIDs] is allowed); have received granulocyte colony stimulating factor (G-CSF) or granulocyte/macrophage colony stimulating factor support within one week before the Screening Visit, or pegylated G-CSF within two weeks before the Screening Visit, or blood transfusion and/or erythropoietin within one week before first dose; have received a cumulative dose of corticosteroid ≥ 150 mg (prednisone or equivalent doses of corticosteroids) within two weeks before the first infusion; no dietary supplements allowed during the trial period, except multivitamins, vitamin D and calcium.
- Surgery/procedures: major surgery within six weeks or open biopsy within 14 days before drug infusion; plan for any major surgery during treatment period; patients not willing or able to have a pre-trial tumor biopsy taken (the screening biopsy can be omitted if archived material is available); presence or anticipated requirement of epidural catheter in relation to infusions (within 48 hours before and after dose of trial drug).

Final 5.0 (incorporating Protocol Amendment 4) 06 Jul 2017

- Central nervous system: any history of intracerebral arteriovenous malformation, cerebral aneurysm, brain metastases or stroke (transient ischemic attack > 1 month prior to screening is allowed).
- Prior therapy: any anti-cancer therapy including small molecules, immunotherapy, chemotherapy monoclonal antibodies or any other experimental drug within four weeks or five half-lives, whichever is longest, before first infusion; prior treatment with bevacizumab within 12 weeks before the first infusion (for anti-cancer therapies with half-lives > 8 days, a washout period of at least 28 days is acceptable); any prior therapy with a conjugated or unconjugated auristatin derivative; radiotherapy within 28 days prior to first dose; patients who have not recovered from symptomatic side effects of radiotherapy or symptoms of autoimmune toxicities related to previous treatment with check-point inhibitors at the time of initiation of screening procedure.
- Other cancer/metastases: known past or current malignancy other than inclusion diagnosis (except for: cervical carcinoma of Stage 1B or less; non-invasive basal cell or squamous cell skin carcinoma; non-invasive, superficial bladder cancer; prostate cancer with a current PSA level < 0.1 ng/mL; breast cancer in BRCA1 or BRCA2 positive ovarian cancer patients; or any curable cancer with a complete response (CR) of > 5 years duration); radiographic evidence of cavitating pulmonary lesions; tumor invading any large blood vessel, unless approved by the sponsor Medical Officer.
- Other: ongoing, significant, uncontrolled medical condition; presence of CTCAE (Common Terminology Criteria for Adverse Events) grade ≥ 2 peripheral neuropathy; clinically significant active viral, bacterial or fungal infection requiring intravenous treatment with antimicrobial therapy starting less than four weeks prior to first dose or oral treatment with antimicrobial therapy starting less than 10 days prior to first dose; known human immunodeficiency virus seropositivity; positive serology (unless due to vaccination or passive immunization due to Ig therapy) for hepatitis B defined by positive test for hepatitis B surface antigen (HBsAg) and/or positive test for antibodies to hepatitis B surface and core antigens (anti-HBs and anti-HBc); positive serology for hepatitis C based on test at screening; inflammatory bowel disease including Crohn's disease and colitis ulcerosa; inflammatory lung disease including moderate and severe asthma and chronic obstructive pulmonary disease (COPD) requiring chronic medical therapy; ongoing acute or chronic inflammatory skin disease.
- Ophthalmological: active ocular surface disease at baseline (based on ophthalmological evaluation); history of cicatricial conjunctivitis (as evaluated by an ophthalmologist).

NUMBER OF PATIENTS: Approximately 46 to 63 patients will be screened to ensure that 32 to 44 patients (anticipated screen failure rate of 30%) complete the trial.

In the Dose Escalation part: 12 to 24 patients are planned to be enrolled: three to six patients per dose level for three dose levels (plus a potential intermediate dose cohort).

In the Cohort Expansion part: 20 to 30 patients are planned to be enrolled in two or three indication arms.

TRIAL TREATMENT(S): Tisotumab vedotin (HuMax-TF-ADC) will be administered as an intravenous infusion over a minimum of 30 minutes on Days 1, 8 and 15 of each cycle (one treatment cycle is 28 days). Each patient's dose will be calculated based on the patient's weight rounded to the nearest kilogram. Preventive eye therapy should be administered in relation to infusions.

The Dose Escalation part will evaluate tisotumab vedotin (HuMax-TF-ADC) at doses of 0.9 mg/kg and up (1.2 and 1.5 mg/kg). The maximum tested dose will be 1.5 mg/kg. Decisions to escalate the dose of tisotumab vedotin (HuMax-TF-ADC) for the next cohort will be based on the safety data obtained from the 3 (+3) patients during their first treatment cycle (28 days). A DMC will evaluate all safety data (including serious adverse events [SAEs], adverse events [AEs] and laboratory data) after each cohort completes Cycle 1.

Patients in the Cohort Expansion part will be treated with the RP2D from the Dose Escalation part. Reduced dose can be administered in accordance with the mitigation strategies or at the discretion of the treating physician based on individual patient observed toxicity profile and quality of life evaluation, and after consultation and agreement by the sponsor Medical Officer.

Severe ocular toxicity has been observed at 1.2 mg/kg 3q4wk. Patients will no longer receive the 3q4wk schedule; instead tisotumab vedotin (HuMax-TF-ADC) 2.0 mg/kg will be administered once q3wk, on Day 1 of each 21-day cycle.

Final 5.0 (incorporating Protocol Amendment 4) 06 Jul 2017

DURATION OF TREATMENT: In the Dose Escalation part the patients will be treated for four cycles or until unacceptable toxicity. After four cycles, if there is evidence of the patient benefiting from treatment, at the discretion of the treating physician on the patient status, there is an option to continue in the trial for up to a maximum of eight additional cycles (32 weeks) or until the patient withdraws from the treatment/trial due to the withdrawal criteria. The treatment period will have a maximum duration of 48 weeks.

In the Cohort Expansion part patients will be treated similarly but up to a maximum of nine cycles (36 weeks, or less after changing to the once q3wk dosing scheme)) or until unacceptable toxicity or disease progression, at the discretion of the treating physician.

At the end of the planned number of cycles, Genmab will ensure provision of continued treatment to patients with clinical benefit defined as stable disease (SD) or better, until unacceptable toxicity or Progressive Disease (PD) is observed.

TRIAL EVALUATIONS:

Primary Endpoint:

• AEs during the trial: incidences of AEs, SAEs, infusion-related AEs, CTCAE grade ≥ 3 AEs and AEs related to trial drug

Secondary Endpoints:

- Safety laboratory parameters (hematology, biochemistry, coagulation factors and flow cytometry)
- Skin disorders
- Bleeding events
- Neuropathy
- PK parameters (clearance, volume of distribution and area-under-the-concentration-time curve $[AUC_{0-Clast}$ and $AUC_{0-\infty}]$), maximum concentration $[C_{max}]$, time of C_{max} $[T_{max}]$, pre-dose values, and half-life of tisotumab vedotin (HuMax-TF-ADC) and free toxin [monomethyl auristatin E, MMAE])
- Immunogenicity of tisotumab vedotin (HuMax-TF-ADC) (human anti human antibodies)
- Anti-tumor activity measured by tumor shrinkage (based on computerized tomography [CT] scan evaluations), change in PSA and CA 125
- Objective Response (CR or Partial Response [PR]), Disease Control (CR, PR or SD), Progression-Free Survival (PFS) and Duration of Response (DoR)

Research Endpoints:

- TF expression in tumor biopsies
- Circulating TF
- Circulating cell-free deoxyribonucleic acid (cfDNA)

STATISTICAL METHODS: No formal statistical tests will be performed; descriptive statistics will be presented. Two-sided 95% confidence intervals will also be calculated. All data will be listed.

The full analysis population will comprise all patients who have been exposed to trial drug and will be used for evaluation of all endpoints.

Further details will be given in a separate Statistical Analysis Plan.

DATE AND VERSION: Version 5.0 (incorporating Protocol Amendment 4) 06 July 2017

2	TABLE OF CONTENTS	
1	SYNOPSIS	4
2	TABLE OF CONTENTS	9
3	LIST OF ABBREVIATIONS AND DEFINITION OF TERMS	16
4	ETHICS	19
4.1	Ethics Committee	19
4.2	Ethical Conduct of the Trial	19
4.3	Patient Information and Consent	19
5	INVESTIGATORS AND TRIAL ADMINISTRATIVE STRUCTURE	20
6	INTRODUCTION	2.2

7	TRIAL OBJECTIVES AND ENDPOINTS	41
7.1	Trial Objectives	41
7.1.1	Primary Trial Objective	41
7.1.2	Secondary Trial Objectives	41
7.2	Trial Endpoints	41
7.2.1	Primary Endpoint	41
7.2.2	Secondary Endpoints	41
7.2.3	Research Endpoints	42
8	INVESTIGATIONAL PLAN	43
8.1	Overall Trial Design and Plan	43
8.1.1	Trial Overview	45
8.1.1.1	Screening Phase (Visit 0)	56
8.1.1.2	Treatment Phase (C1 to CX)	56
8.1.1.3	Unscheduled Visit (U1 to UX)	57
8.1.1.4	Follow-up Phase	57
8.1.1.5	End of Trial Visit (EOT)	57
8.1.1.6	Safety Follow-up Visit.	57
8.2	Trial Duration and End of Trial	58
8.2.1	Trial Stopping Criteria	58
8.3	Trial Population	59
8.3.1	Inclusion Criteria	59
8.3.2	Exclusion Criteria	62
8.3.3	Patient Allocation Procedure	65

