8.3 Trial Population

The patient population in the Dose Escalation part will encompass patients with advanced (locally advanced and/or metastatic) cancer of the ovary, cervix, endometrium, bladder, prostate (CRPC), esophagus or lung (NSCLC) who have failed available standard treatments or who are not candidates for standard therapy.

The specific indications for the Cohort Expansion part will be decided once the RP2D has been determined. The inclusion and exclusion criteria for a reduced number of previous lines of treatment will be specified for all potential indications.

The Dose Escalation part of the trial is planned to be performed in a maximum of three sites in Denmark, UK and the USA. The Cohort Expansion part of the trial is planned to be performed in the ongoing countries and in Hungary and Belgium.

Thirty two to 44 patients are planned to be enrolled in the trial. Assuming an anticipated screen failure rate of 30%, 57 to 76 patients will be screened in total.

- In the Dose Escalation part: 12 to 24 patients are planned to be enrolled: three to six patients per dose level for three dose levels (plus a potential intermediate dose cohort).
- In the Cohort Expansion part: 20 to 30 patients are planned to be enrolled in two or three indication arms.

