8.3.4.2 Criteria for Patient Withdrawal from the Trial

Patients will be withdrawn from the trial at any time for any of the following reasons:

- Patient choice.
- Investigator or sponsor decision.
- Initiation of new anti-cancer treatment.
- Lost to follow-up.
- Intercurrent illness that precludes further participation or requires a prohibited concomitant treatment.
- Disease progression.

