8.3.4.5 Replacement of Patients

Patients who discontinue the trial during the first cycle (28 days) for reasons other than a DLT should be replaced. After implementation of the urgent safety measure (Protocol Amendment 4), no patients will be replaced.

Patients who are withdrawn after the first cycle will not be replaced. However, sufficient number of patients will be enrolled to ensure the minimum sample size defined (see Section 12.9).

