12.3 Statistical Methods

The presentations will be done separately for the Dose Escalation part and the Cohort Expansion part.

In the reporting of the Dose Escalation part tables will report by cohort, while in the Cohort Expansion part tables will report by indication.

The shift from the 3q4wk dosing to the once q3wk dosing in the Cohort Expansion part may lead to a need for reporting some tables by dosing schedule. This will be described as appropriate in the SAP.

No formal statistical tests will be performed.

For efficacy analyses, the quartile estimates of PFS and DoR from the Kaplan-Meier product limit algorithm will be presented (Kaplan and Meier, 1958). The 2-sided 95% confidence interval will be presented as well. The number of events may be small, and thereby limit use of the Kaplan-Meier method to provide reliable information. In this case, descriptive statistics (e.g., n, mean, standard deviation, median, minimum and maximum) for PFS or DoR will be presented. Objective response (CR or PR) rate will be determined along with the corresponding 2-sided 95% exact binomial confidence interval.

All data will be listed. Baseline is defined as the latest available measurement made before the first treatment with tisotumab vedotin (HuMax-TF-ADC).

A patient will be considered as having completed the trial when all planned trial visits have been performed.

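### The synopsis presents 32 to 44 patients as trial completers, but its screening numbers allow for no loss after enrolment and deliver that number enrolled, not completed

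*Protocol*

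**What the plan says.** Protocol Section 1, in its paragraph on patient numbers, states: "Approximately 46 to 63 patients will be screened to ensure that 32 to 44 patients (anticipated screen failure rate of 30%) complete the trial". The only loss it names is screen failure. The next lines give the part sizes as enrolment figures: "In the Dose Escalation part: 12 to 24 patients are planned to be enrolled", and 20 to 30 in the Cohort Expansion part.

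Protocol Section 8.3 uses the same range for a different quantity: "Thirty two to 44 patients are planned to be enrolled in the trial". It continues: "Assuming an anticipated screen failure rate of 30%, 57 to 76 patients will be screened in total".

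Completion is a defined term. Section 12.3: "A patient will be considered as having completed the trial when all planned trial visits have been performed".

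Section 8.3.4.2 opens: "Patients will be withdrawn from the trial at any time for any of the following reasons". Its list includes disease progression, new anti-cancer treatment, loss to follow-up, intercurrent illness and patient choice. These are withdrawals from the trial; withdrawal from treatment has its own list in Section 8.3.4.1.

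Section 8.3.4.5 replaces patients who discontinue in the first cycle for reasons other than a DLT, and does not replace those withdrawn later. It adds: "After implementation of the urgent safety measure (Protocol Amendment 4), no patients will be replaced". It then promises that a "sufficient number of patients will be enrolled to ensure the minimum sample size defined (see Section 12.9").

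**The concern.** The synopsis gives an assurance about completers, and its arithmetic holds only if every enrolled patient completes. The protocol's own rules make that implausible: a patient who progresses before the last planned visit leaves the trial and, under Section 12.3, is not a completer.

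Eligibility requires relapsed, advanced and/or metastatic disease and a life expectancy of at least three months. Planned visits run for about 27 weeks in the Cohort Expansion part on the 21-day schedule. In the Dose Escalation part they run for at least about 44 weeks (16 of treatment, up to 24 of follow-up, 4 to the End of Trial visit).

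At stake is the accuracy of a headline design statement. An ethics committee or investigator reading only the synopsis would expect 32 to 44 patients observed through the whole visit schedule.

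**Working it through.** **Inputs.** Screened 46 to 63 and completing 32 to 44 (Section 1). Screen failure 30% (Sections 1, 8.3 and 12.9). Enrolled 32 to 44 (Section 8.3). Part sizes 12 to 24 and 20 to 30 (Section 1). Loss after enrolment: not stated, so varied below as an assumption.

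**Step 1: reproduce the stated figure.** Screened = n / (1 − 0.30), rounded up.
- 32 / 0.70 = 45.7, giving 46.
- 44 / 0.70 = 62.9, giving 63.

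Both ends match exactly. In reverse, 46 × 0.70 = 32.2 and 63 × 0.70 = 44.1. Screen failure accounts for the whole difference, so the implied loss after enrolment is 0%.

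Section 12.9 uses the same calculation for the Dose Escalation part, there explicitly from enrolment: 12 / 0.70 = 17.1, giving 18, and 24 / 0.70 = 34.3, giving 35, which are its stated 18 to 35.

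**Step 2: allow for loss.** With 32 and 44 enrolled and loss d, expected completers = n × (1 − d). Screening needed to obtain 32 and 44 completers = n / (1 − d), rounded up, then divided by 0.70 and rounded up.

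| Assumed loss d | Completers from 32 / 44 enrolled | Screened for 32 / 44 completers |
|---|---|---|
| 0% | 32 / 44 | 46 / 63 |
| 5% | 30.4 / 41.8 | 49 / 68 |
| 10% | 28.8 / 39.6 | 52 / 70 |
| 20% | 25.6 / 35.2 | 58 / 79 |
| 30% | 22.4 / 30.8 | 66 / 90 |
| 50% | 16.0 / 22.0 | 92 / 126 |

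If each patient independently had a 10% chance of leaving, the chance that all complete would be 0.9^32 = 3.4% or 0.9^44 = 1.0%.

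**Step 3: could a lower screen failure rate absorb the loss?** With 10% loss, the screen failure rate would have to be 1 − 32 / (46 × 0.9) = 22.7% at the lower end and 1 − 44 / (63 × 0.9) = 22.4% at the upper end. The protocol plans on 30%.

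**Step 4: the totals in the same sentence.** Section 8.3's 57 to 76 does not follow from 32 to 44 at 30%: 57 × 0.70 = 39.9 and 76 × 0.70 = 53.2 enrolled. The parts sum to 12 + 20 = 32 and 24 + 30 = 54, and 54 / 0.70 = 77.1, giving 78 screened. The upper total of 44 is below the sum of the part maxima.

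**Step 5: the promised minimum.** Section 12.9 gives a maximum of 24 for the Dose Escalation part and up to 20-30 for the Cohort Expansion part. It labels neither as a minimum. A Cohort Expansion minimum of 20 is stated in Section 1 under the trial design.

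**The case against.** The strongest reply is that this is a slip of one verb. Section 8.3 and the part sizes within the synopsis itself speak of enrolment, Section 12.9 sets no completer target, and if 32 to 44 means enrolled then 46 to 63 is correct at 30% screen failure. That is the likely cause, and it stands. But *complete* is defined in Section 12.3, and the sentence claims to ensure it, so the statement is wrong as written.

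It may also be said that Section 8.3.4.5 promises sufficient enrolment. That promise carries no loss allowance, and at 30% screen failure any extra enrolment would need more than 46 to 63 screened. Nor can Section 8.3's 57 to 76 be read as a hidden attrition allowance: that section names only screen failure and calls 32 to 44 enrolled.

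Stronger conclusions are tempting, but the documents do not support them:
- **That PFS and DoR will rest on a small fraction of patients.** Section 12.5.3.3 derives PFS for all patients, and a patient leaving at progression supplies a PFS event. DoR (Section 12.5.3.4) also ends at progression or death and depends on the number of responders.
- **That the primary objective is undermined.** Section 7.1.1 asks for tolerability, without a long-term qualifier. The endpoint is AE incidence, and Section 12.2 analyses all exposed patients. MTD decisions use Cycle 1 data.
- **That only some 6 to 14 of 32 would complete.** That follows from an assumed exponential PFS with a median of 3 to 6 months; the documents give no PFS figure. It also applies 27 weeks to all Cohort Expansion patients, although Section 8.1 allows up to 36 weeks for those who began on 28-day cycles.
- **That no minimum sample size exists.** Section 1 states one for the Cohort Expansion part; the fault is the reference to Section 12.9.

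**Conclusion.** The point holds as an overstated size in the synopsis. The zero allowance for loss follows from the protocol's own numbers and needs no assumption. The design delivers 32 to 44 patients enrolled.

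The size of the shortfall does depend on an assumed loss rate: about 29 to 40 completers at 10%, and 16 to 22 at 50%. That loss will exceed 10% is a judgement from the eligibility criteria and the progression rule, not a figure in the protocol.

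No planned estimate or interval uses the number of completers, and there is no formal test or power calculation for it to affect. The consequence is confined to what the headline statement leads readers to expect about follow-up through all planned visits.

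**What to change.** 1. In the synopsis, Number of Patients, replace *complete the trial* with *are enrolled and exposed to trial drug*, which matches the population in Section 12.2.
2. In the same edit, reconcile the totals: 46 to 63 screened against 57 to 76 in Section 8.3, and the upper enrolment of 44 against 24 + 30 = 54.
3. In Section 8.3.4.5, correct the reference to a minimum in Section 12.9. Point instead to the Cohort Expansion minimum of 20 in Section 1 and state that it counts exposed patients.

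No expected-completer range or assumed median PFS needs to be added, since no analysis would use it. The cost is wording only: no extra patients and no change to any analysis. The stated size becomes less favourable but accurate.
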